A.1.a. Increasing prevalence of cannabis-tobacco co-use. Cannabis and tobacco are frequently used together (10-19) and co-use may occur in several forms; such as, simultaneous use (cigar wrappers filled with cannabis ‘blunts’), sequential use (‘chasing’ cannabis with tobacco), for substitution purposes (using one when the other is not available), or in an asynchronous manner. While the overall rates of cannabis and tobacco co-use in the US appear to have increased modestly (~18%) from 4.4% in 2003 to 5.2% in 2012 (20), the prevalence of daily cannabis use among daily cigarette smokers has nearly doubled from 4.9% in 2002 to 9.0% in 2014 (21). One out of every 14 daily cigarette smokers (aged 26+) are daily cannabis users, while among those aged 18-25, one out of every five daily cigarette smokers are daily cannabis users. For comparison, one out of every 100 never cigarette smokers are daily cannabis users (21). This increase may be partially explained by the overall increase in cannabis use in the US. Rates of past month cannabis use for adults increased from 10.7% in 2002 to 14% in 2016, with substantial increases occurring among adults aged 26 and over (4% in 2002 to 7.2% in 2016), while use rates among 18-25 year olds remain high (20.8%) (22). Increases in cannabis use prevalence are in large part due to the reduced perception of harm, its perceived and real medical benefits and relaxed cannabis legislation (23-26). These factors are likely to lead to further increases in cannabis use and may result in continued increases in the co-use of cannabis and tobacco.

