B1. Study Overview. This proposed prospective tobacco cessation study will evaluate the impact of concurrent cannabis use and severity on tobacco abstinence among co-users and assess changes in cannabis use during treatment. Adult tobacco users (ages 18-40) who are motivated to quit smoking will be recruited. Cannabis co-users will be oversampled (2:1) and will be compared to tobacco only participants (using appropriate propensity score models). All participants will receive first-line tobacco cessation pharmacotherapy (varenicline) paired with a behavioral intervention to bolster abstinence rates (contingency management and psychosocial counseling) for a standard 12-week treatment period. Cannabis use will not be targeted with treatment. This is not a treatment outcome study per se and thus we are not evaluating (with a control group) an intervention. Rather, cannabis use status (co-use vs. not) is our independent variable. Biochemical verification of tobacco and cannabis use will be collected at screening and throughout the 12-week treatment period in addition to daily self-reports of use. Specifically, this study will: 1) examine the impact of cannabis co-use on tobacco cessation among co-users compared to tobacco only users (Aim #1); 2) with the use of frequent measurement, assess changes in cannabis use (among co-users) during tobacco treatment and determine if profiles of changes in cannabis use emerge (i.e., compensatory use, reduction, no change) (Aim #2); and 3) assess for a dose-dependent impact of cannabis use severity on tobacco cessation outcomes among co-users (Exploratory Aim).

It should be noted that while this is not a randomized and blinded study (cannabis co-use status will be known to research staff), it is important to not bias the results of the study. The hypothesis is that cannabis co-use will adversely impact tobacco cessation, but it's important to the scientific integrity of this study to obscure that hypothesis from study participants and manage biases with research staff. Staff will be educated about introducing bias into the study and methods to manage bias in non-randomized and non-blinded trials. For research participants, the aim of the study will intentionally broad and ambiguous to not

overtly influence their behavior and tobacco quit attempt. The title of the study and consent document, therefore, are not as specific as they would normally be to maintain the integrity of this research.

B2. Preliminary Studies.

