Biochemical Verification of Tobacco, Cannabis, and Other Substances: At each study visit, a urine sample will be collected and an instant-read urine drug screen will be conducted, which includes a qualitative urinary cannabinoid test (cut-off of 50 ng/ml) to determine cannabis use status, as well as assays for other commonly used substances (amphetamines, opioids, etc.). Urinary cotinine (a metabolite of nicotine) will be the primary indicator of tobacco abstinence (83). Qualitative urinary cotinine will be tested via instant-read, immunoassay test strips for purposes of contingency management. Urine samples will be aliquoted and delivered to the laboratory for determination of quantitative cotinine levels. Abstinence criteria for quantitative cotinine will be set at 80 ng/ml. Urinary quantitative cannabinoid values (11-nor-9-carboxy- Δ 9-tetrahydrocannabinol; THCCOOH) will be tested at MUSC. Urine creatinine will also be obtained, to allow for creatinine-normalized urine cannabinoid levels. Saliva samples will be collected for 10 study participants at one time point. A saliva sample may be collected in addition to other biochemical measures for quality improvement purposes and will not be used for research purposes.

Substance Use Assessments: Several substance use assessments will be conducted throughout the study, including; detailed use history (for all substances), dependence level, motivation to quit (tobacco and cannabis), craving, withdrawal, satisfaction and subjective effects (cannabis and tobacco), and motives for use (full listing in Table 2). TLFB procedures (84) will be used at screening (30-day calendar) to assess the frequency and quantity of tobacco use (cigarettes per day and other tobacco use), cannabis, alcohol and other drug use. In order to determine an individual-specific cannabis unit, cannabis quantification procedures will be conducted at screening and as needed when new methods of cannabis use are endorsed. For plant material-based methods, grams of cannabis will be estimated using a surrogate substance (78).

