Participants are asked to show research staff the average amount of cannabis that they use (with the surrogate) for each combustible modality endorsed (e.g., joints, blunts) and report the estimated dollar amount associated with that quantity. The surrogate substance is then weighed on a scale to determine average grams per method. That amount then serves as the individual's standard unit (e.g., "standard blunt") for future reporting. This quantification procedure has been successfully implemented previously (85, 86), is being used in an ongoing study at MUSC (R01 DA038700), and has been shown by our team to improve the predictive validity of clinical outcomes (87). The gram estimation procedure will not work for non-plant based cannabis use methods, which are challenging to quantify. We will quantify these non-combustible methods with techniques used in an ongoing study (R01 DA038700). We will assess times used or hits taken (waxes, dabs, concentrates, lotions), milligrams ingested (edibles, drinks), and milliliters used (oils, tinctures, liquids). We expect that non-combustible methods will continue to evolve and we will modify our procedures accordingly.

Safety Assessments and Medication Adherence: Adverse events will be systematically collected at all visits and will be coded in Medical Dictionary for Regulatory Activities (MedDRA) terms. Medication adherence will be monitored through several methods; pill counts, smart bottle caps, daily self-report of doses taken through the daily diaries, and review of medication videos submitted through REDCap.

EMA measures: EMA items will include 10-30 items assessing cannabis use, tobacco use, and cannabis-tobacco co-use and relevant variables related to co-use relationships. At each EMA session signal, participants will be asked to report whether they have used cannabis, tobacco, or both substances since the previous assessment. Branching logic will be used to administer follow-up items on quantity and frequency of use since the previous assessment, subjective effects, cannabis intoxication, tobacco craving, etc. Each assessment is expected take 1-3 minutes to complete.

Table 2. Assessment Schedule

Study Week →	SC	T	Treatment Phase												F/U	
	M	1	2	3	4	5	6	7	8	9	10	11	12	16	26	
Informed Consent/Demographics	X															
Locator Form and Updates	X	X	X	X	X	X	X	X	X	X	X	X	X	X	X	X
Medical/Psychiatric Assessments																
Medical History and Physical Exam	X															

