Participant Compensation: Participants will be compensated \$40 for the Screening visit and \$30 per visit for Training, Day 0, other weekly visits (13 visits) and/or early termination (ET) that occurs at any point other than during the Week 12 window (\$50 for Week 12 window visits). They will be compensated \$50 for the end-of-treatment visit (Week 12), and \$50 for the 6-month follow-up visit (Week 26). Compensation is based on completion of all study procedures. Partial compensation may be given for partially completed study visits. For example, payment amounts for remote visits will be contingent on return of the urine sample to study staff at the next in-person study visit. Compensation will be delivered contingent on tobacco abstinence at weekly visits starting at Week 2 (\$20 per visit; \$220 possible). Participants will be compensated for completing daily dairies and medication videos during the 12-week treatment phase. Compensation amount for remote surveys and videos will be based on the percentage of videos and morning reports completed over the past week and will be paid at weekly visits. The compensation scheduled based on the percentage of completed sessions is shown to the right (\$300 maximum for $\geq 90\%$ compliance over 12 weeks). Participants may earn a total of \$1,050 for study participation and completion of all study procedures.

Medication Videos and Logs (% completed each week)	Payment
90-100% compliance	\$25
80-89.9% compliance	\$20
70-79.9% compliance	\$15
50-69.9% compliance	\$10
30-49.9% compliance	\$5
<30% compliance	\$0

Payment for study visits will be made using a pre-paid debit card, called a ClinCard. It works like a bank debit card and participants may use the card to purchase goods or services everywhere Debit MasterCard is accepted. Participants will be given or mailed a ClinCard at the beginning of the study. Each time they receive payment for participation in this study, the money will be added to the card, as outlined in the payment schedule above. Details of the debit card system are explained on an additional sheet.

If an Unscheduled Visit is required during study participation, the participant will be compensated \$10/visit in return for the time and travel demands asked of them.

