10.0 Statistical Analysis and Data Management

Analytic Strategy.

Power and sample size. The proposed study is powered to detect a meaningful difference in end of treatment tobacco abstinence between cannabis co-users and tobacco only users. Secondarily, the study will assess the relationship between cannabis use patterns during treatment and nicotine dependence severity in co-users. Specific Aim #1: Examine the impact of cannabis co-use on tobacco cessation outcomes among co-users compared to tobacco only users. Hypothesis 1: Co-users will have lower rates of 7-day point prevalence abstinence from tobacco at the end of treatment (Week 12) compared to tobacco only users. In a cross-sectional survey of national household data (51), tobacco cessation was reported among 65.5% of respondents who endorsed no cannabis use as compared to 21.8% of tobacco cessation in those reporting current cannabis use ($\Delta=43\%$). Studies examining the efficacy of varenicline for tobacco cessation (108, 109) noted near 50%-point prevalence abstinence at treatment conclusion (Week 12) in the varenicline-treated group. Finally, in our recently completed adolescent varenicline trial (U01 DA0317779), youth cannabis co-users reported point prevalence tobacco abstinence in 20% of participants at Week 12 and 43% in those who use tobacco only (analysis with all available data). The proposed R01 study intends to apply a successful tobacco treatment (varenicline) paired with contingency management in treatment-seeking smokers. Assuming a similar abstinence rate in tobacco only users (45%) and a successful abstinence rate in participants who are cannabis co-users as compared to the adolescent study (20%; $\Delta=25\%$), to achieve 80% power with a 5% type 1 error rate, a sample of 82 participants in the cannabis co-using cohort and 41 in the tobacco only cohort. However, to account for the inclusion of 2 study sites in the design, an additional fixed factor of site will be included in the analytic models. Although we hope that equal proportions of co-users and non co-users present at each site, we understand that the fundamental differences between the Charleston metro area, Pickens County SC, and Florence exist and may cause some correlation between co-use group and study site. Assuming that the proportion of variance in co-use groups due to study site and other covariates may be moderate ($R^2=0.25$) and that attrition will not exceed 25%, we have adjusted our study sample size to account for this scenario. This increases our randomized sample to a total of 208 (139 cannabis co-users and 69 tobacco only users) accounting for both site correlations with co-use group and anticipated attrition. If site correlations with study outcomes or attrition are lower than pre-specified, our statistical power will exceed 80%. Specific Aim #2: Among co-users, assess changes in cannabis use during tobacco cessation treatment. Hypothesis 2: Co-users with moderate to high severity of nicotine dependence will demonstrate increases in concurrent cannabis use, while lower severity of nicotine dependence will yield no changes in cannabis use. To attain adequate power to assess Aim #2, a within co-use cohort comparison, the study will oversample the cannabis co-use cohort as compared to the tobacco only cohort (2:1). At screening, nicotine dependence will be assessed via the Fagerström Test for Nicotine Dependence (FTND) (92) and categorized accordingly: low nicotine dependence (0-4), medium or high nicotine dependence (5-6; 7-10). Cannabis use during the final 4 weeks of study treatment as compared to baseline use will be assessed among co-users. Based on our preliminary data from an ongoing adult tobacco cessation trial (R34 DA042228), we have nearly equivalent numbers of participants falling into low and moderate/high nicotine dependence categorizations (Mean=4.5; Median=5). Therefore, we anticipate ~40% will have medium/high nicotine dependence. With 208 participants, 139 in the cannabis co-use cohort (104 completers), we will achieve 80% power with a type 1 error rate of 5% to detect a between group cannabis use difference of Cohen's $d\approx0.6$ (Med/High nicotine dependence vs. low nicotine dependence).

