Primary Study Aims: Aim 1: To assess the difference in the log-odds of abstinence from tobacco at the end of treatment (Week 12) between baseline cannabis co-users compared to tobacco only participants, augmented inverse probability weighted logistic regression models will be developed. The inverse of the conditional probability of being in the cannabis co-use cohort will be included in the model to account for inherent imbalances between study groups and to reduce bias by resembling a randomized controlled trial. In addition to the inverse propensity weights, AIPW methods incorporate a covariate and study site adjusted model for the study group outcome (114). Aim 2: To assess the association of baseline nicotine dependence severity (Med/High nicotine dependence vs. low nicotine dependence) with cannabis use rates during study treatment, generalized linear mixed effects models will be assessed with cannabis use rates and amounts during the final 4 weeks of treatment as the primary indicator of cannabis use severity and nicotine dependence group as the primary model predictor. In addition to grouping by nicotine dependence severity, continuous levels of dependence severity (FTND score) will be modeled to assess possible linear and quadratic relationships between dependence severity and cannabis use. Following examination of the differences in end of treatment cannabis use rates based on baseline nicotine dependence, rates of cannabis use will be assessed by group (nicotine dependence severity) over all weekly study visits to determine if those with increased dependence severity exhibit a different trajectory (slope and pattern) of cannabis use during the entire study treatment. Model-based means and associated standard errors will be used to test group level differences. Exploratory Aim: To assess the relationship between baseline cannabis use severity and tobacco outcomes, generalized linear mixed effects models will be developed with weekly 7-day point prevalence abstinence from tobacco as the primary model outcome. In addition to tobacco abstinence, weekly average cigarettes per day will be examined as an indicator of use reduction differences over time. Longitudinal patterns in tobacco abstinence and use amounts will be modeled through the inclusion of baseline cannabis use severity indicators, study visit, and baseline tobacco use rates as model covariates. Additionally, differential effects over time will be examined with the inclusion of the interaction of cannabis use severity and study visit. Model-based means and associated standard errors will be used to test group level differences across the study treatment.

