
Secondary Data Analysis: In addition to end of treatment point prevalence tobacco abstinence rates, similar analytic models will be used to assess abstinence rates at the 6-month follow-up visit. Additionally, longitudinal analysis of weekly tobacco abstinence will be assessed using repeated measures logistic regression models using a general estimating equations framework (GEE) (115) and working correlation

structures will be independently compared using the quasi-likelihood under the independence model criterion statistic (116). Similarly, the number of smoking days per week and cigarettes per day will be collected via daily diaries and compared between co-use cohorts using generalized linear mixed effects regression models. Finally, weekly cannabis and tobacco use will be collected to develop group-based trajectory models and time naïve covariates will be used to determine group membership. Additionally, changes in cannabis craving, withdrawal, use, and subjective effects during treatment with varenicline will be examined in the cannabis co-use group. Specifically, changes in cannabis craving, withdrawal (synchronous effects of varenicline) and cannabis use severity (substitution) will be assessed for correlations with changes in tobacco use. Generalized linear mixed effects models will be developed with cannabis use outcomes and the time varying effects of tobacco use as the primary independent variable. Further, noting possible differences in the relationship between tobacco outcomes and combustible/non-combustible cannabis use, model effect modification will be assessed using cannabis use type groupings (primarily combustible vs. primarily non-combustible). All analyses will be conducted using SAS version 9.4 (SAS Institute, Cary, NC, USA).

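### Aim 2 pools blunts with tobacco-free cannabis, so total cannabis use cannot separate no change from a product switch, or compensation from differential quitting of blunts

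*Combined protocol and SAP*

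**What the plan says.** **Premise.** Section 2.0, B1 (Study Overview) states: "Cannabis use will not be targeted with treatment". A.2.b in the same section frames compensation as increased use of the substance that is not being treated. Neither place makes an exception for blunts.

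**Blunts.** Section 2.0, A.1.a gives blunts ("cigar wrappers filled with cannabis") as its example of using both substances at once. Section 9.0 (Substance Use Assessments) expects them: staff obtain a weighed standard unit "for each combustible modality endorsed (e.g., joints, blunts").

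**What is treated and rewarded.** All participants receive varenicline and counselling for tobacco. Section 9.0 (Participant Compensation) adds: "Compensation will be delivered contingent on tobacco abstinence at weekly visits starting at Week 2", at $20 a visit and up to $220. The test behind the reward is described under Biochemical Verification: "Qualitative urinary cotinine will be tested via instant-read, immunoassay test strips for purposes of contingency management".

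**Analysis.** Section 10.0 (Primary Study Aims, Aim 2) specifies mixed models "with cannabis use rates and amounts during the final 4 weeks of treatment as the primary indicator of cannabis use severity", with nicotine dependence group as the main predictor. The only split by product is in Secondary Data Analysis, as an effect modifier: "primarily combustible vs. primarily non-combustible". Blunts and joints both fall on the combustible side.

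**The concern.** A blunt is cannabis use and tobacco use at once. A co-user who stops tobacco, or who wants a negative cotinine strip, has a reason to drop blunts that has nothing to do with substitution. Two readings of Aim 2 then become ambiguous.

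- **An unchanged total.** It could mean that nothing changed, or that blunts fell while joints, vaped or edible cannabis rose by the same amount. The planned outcome gives the same answer for both.
- **A dependence-group difference.** If low-dependence co-users quit tobacco more often and drop more blunts, end-of-treatment cannabis use will be lower in that group. The medium/high group then looks relatively higher, which is the direction of Hypothesis 2, although nobody has increased use.

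At stake is the interpretation of the Aim 2 result. The tobacco endpoint and the payment rule are not in question.

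**Working it through.** **Inputs from Section 10.0, Power and sample size.** 139 co-users; 25% attrition; 104 completers (139 × 0.75 = 104.25); about 40% with medium/high dependence, so about 42 against 62; planning abstinence in co-users 20%. The claim is that "we will achieve 80% power with a type 1 error rate of 5% to detect a between group cannabis use difference" of Cohen's d about 0.6. Sidedness is not stated; two-sided is assumed.

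**The plan's own figure.** d = (1.960 + 0.842) × √(1/41.6 + 1/62.4) = 0.561 (0.566 with the t distribution). This agrees with the stated value of about 0.6, so the sample size is not at issue.

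**Unchanged total.** Let b be the blunt share of baseline use and r the fractional fall in blunts. The total is unchanged when tobacco-free use rises by c = b × r / (1 − b). With b = 0.4 and r = 0.3, c = 0.12 / 0.6 = 20%. On a baseline of 100 units, blunts go from 40 to 28 and tobacco-free use from 60 to 72, total 100. A person who changes nothing also totals 100.

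**Group difference with no compensation.** The documents give no blunt share, no abstinence by dependence group and no SD of cannabis use. Assumptions:

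- abstainers drop all blunts and do not switch product; nobody else changes;
- blunt share b is 0.25 to 0.75;
- mean baseline use divided by the SD (m) is 1 to 2;
- overall co-user abstinence stays at 20%, for example 0.6 × 25% + 0.4 × 12.5% = 20%.

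Difference in SD units = b × (abstinence in low − abstinence in medium/high) × m. For 25% against 12.5% this runs from 0.25 × 0.125 × 1 = 0.03 to 0.75 × 0.125 × 2 = 0.19. Rejection rates use the noncentral t with 102 degrees of freedom and standard error √(1/42 + 1/62) = 0.200.

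| Abstinence, low vs medium/high | Difference (SD) | Rejection at nominal 5% |
|---|---|---|
| 20% vs 20% | 0 | 5% |
| 25% vs 12.5% | 0.03 to 0.19 | 5% to 15% |
| 30% vs 5% | 0.06 to 0.38 | 6% to 46% |
| 33% vs 0% | 0.08 to 0.50 | 7% to 70% |

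The last two rows need a very large abstinence gap, and their upper ends also need the largest blunt share and the largest m.

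**The case against.** The strongest reply is that Aim 2 is about cannabis use as such. Section 2.0, A.2.b worries that quitting tobacco may lead to more cannabis use and its harms. For that question, 40 + 60 becoming 28 + 72 really is no change. **This stands.** A reader might infer that the pooled outcome hides true compensation and that Hypothesis 2 should be tested on tobacco-free cannabis instead. The documents do not support that. The break-even is a true null for total use, and a test on tobacco-free cannabis alone would count a move from blunts to joints as compensation.

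A reader might also infer that the trial would deliver false support for Hypothesis 2. That goes too far. The hypothesis predicts an increase in medium/high dependence and no change in low dependence; in the scenario above, use falls or stays level in both groups. Section 10.0 compares the final four weeks with baseline and models weekly trajectories by dependence group, so the direction would be visible. The difference in total use would also be real; only calling it compensation would be wrong.

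Large rejection rates can be produced. A 60% blunt share, falls in blunts of 50% against 20%, and an SD of change of half the baseline mean give 0.6 × 0.3 / 0.5 = 0.36 SD and about 44% rejection. If those falls come from quitting, overall abstinence would be (62 × 50% + 42 × 20%) / 104 = 38%, against the planned 20%.

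Further limits also stand:

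- No passage says that low-dependence co-users quit more; an equal fall leaves the group contrast intact.
- Exclusion criterion (e) in Section 4.0 bars regular use of other tobacco products. It does not name blunts, but may limit how many regular blunt users enrol.
- That the reward acts on blunts is an inference. It depends on cotinine as a whole, so it bears mainly on people who also stop cigarettes, and the strip's cut-off is not given.
- Switching from blunts to joints would shrink the effect on the total.

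Secondary Data Analysis does relate cannabis outcomes to time-varying tobacco use, but no planned analysis isolates blunts.

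**Conclusion.** The point holds as a limit on interpretation. Aim 2 reads change in total cannabis use as change in an untreated substance, while one component contains the treated substance and may fall with it. Neither the Aim 2 outcome nor the combustible split can show this.

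The size cannot be fixed from the documents. With co-user abstinence at the planned 20% and no compensation, the chance of a significant group difference is 5% if abstinence is equal across dependence groups and roughly 5% to 15% under a modest gap of 25% against 12.5%. This rests on the assumed blunt shares (25% to 75%), the assumed ratio of mean to SD (1 to 2) and complete dropping of blunts by abstainers without switching. It is a cheap improvement to the plan; it does not call for a different tested outcome.

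**What to change.** In Section 10.0, Aim 2:

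1. Keep total cannabis use, compared with baseline, as the tested outcome.
2. Prespecify supportive analyses, by dependence group, of tobacco-containing cannabis (blunts and other tobacco-mixed forms) and tobacco-free cannabis, with baseline blunt use (yes/no) as a covariate.
3. Add a tobacco-containing versus tobacco-free grouping to the effect-modification analysis in Secondary Data Analysis.
4. State the reading rule in advance: a result is called compensation only if total use rises from baseline. A rise in tobacco-free use offset by a fall in blunts is described as a switch of product.

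The cost is SAP wording and the derivation of two outcomes from product-level reports that Section 9.0 already plans to collect. No visit, treatment or payment changes. The downsides are two more reported outcomes, and little baseline information on tobacco-free use from co-users who use only blunts.
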